13.6.6 Assessment of Outcome

Event outcome at resolution or time of last follow-up will be recorded as: recovered, recovering, not recovered, recovered with sequelae, fatal, or unknown.

13.7 Adverse Event Reporting Procedures

13.7.1 All Adverse Events

Any clinically significant adverse event that is ongoing at the time of study completion or early termination will be followed by the Investigator until event resolution, the adverse event is otherwise explained, not considered clinically significant by the Investigator, or the patient is lost to follow-up.

All non-serious AE identified will be recorded in the Adverse Event eCRF beginning from the time of first study drug infusion and ending at Extension Day 785 or 84 (± 3) days after last dose of study drug if patient is early terminating or if missed doses are made up. All SAE identified will be recorded in the Adverse Event eCRF beginning from the time of first study drug infusion and ending at Extension Day 785 or 84 (± 3) days after the last dose of study drug if patient is early terminating or if missed doses are made up. Whenever appropriate, the CTCAE (version 5.0 or most current version) should be utilized for naming common AE ([Appendix 19.3](#)).

13.7.2 Serious Adverse Event Reporting

In the event of any SAE reported or observed during the study, whether or not attributable to the study drug, site personnel will report it immediately (within 24 hours of becoming aware of the SAE) by telephone or email to the Sponsor, Allakos, Inc.

Serious adverse event report forms will be provided to the investigational site to assist in collecting, organizing, and reporting SAE, and forms should be completed with as much

information as is available and submitted to the Sponsor within 24 hours. Serious adverse events should also be recorded on the Adverse Event eCRF and designated as “serious.”

Even when only minimal information is available for the initial SAE report, the Investigator should try to make a causality assessment, as the causality is used to determine the timing of regulatory reporting requirements. If the Investigator or designee is not available to sign the SAE report on initial submission, they should be contacted via telephone and their assessment documented on the SAE form (with a note stating signature is forthcoming).

The Investigator may change their causality assessment based on follow-up information and submit an amended SAE report form. All efforts will be made to obtain accurate and complete medical records for the SAE. All efforts to obtain information should be documented in the patient source documents.

The site will notify the Institutional Review Board (IRB) according to its guidelines.

The patient’s condition will be followed by the Investigator or designated Subinvestigator until resolution of the condition or a return to baseline levels. If additional visits are required, the patient will be asked to return to the study site for further follow-up. If the condition is still ongoing at the time the patient exits the study, every effort will be made to continue to follow up with the patient for a reasonable period of time, as determined by the Investigator or until there is a return to baseline or stabilization of the condition. As additional information becomes available, such as hospital discharge notes and patient medical records, the Investigator will be notified and provided with all relevant information.

All SAE that have not resolved by the end of the study or that have not resolved on discontinuation of the patient’s participation in the study must be followed until any of the following occurs:

- The event resolves.
- The event stabilizes.
- The event returns to baseline, if a baseline value is available.
- The event can be attributed to agents other than the investigational product or to factors unrelated to study conduct.
- It becomes unlikely that any additional information can be obtained (patient or health care practitioner refusal to provide additional information, lost to follow-up after demonstration of due diligence with follow-up efforts).

Serious adverse events must be reported within 24 hours to:

Serious Adverse Event Reporting

[contact]

[contact]

E-mail: [contact]

13.7.3 Pregnancy Reporting

Pregnancies are captured if they occur in female patients or in the sexual partners of male patients from the time the patient is first exposed to the investigational product through Extension Day 785 or 84 (± 3) days after last dose of study drug if early termination or if missed doses are being made up.

Female patients must be instructed to discontinue all study drugs and inform the Investigator immediately if they become pregnant during the study. Male patients must be instructed to inform the Investigator immediately if their partner becomes pregnant during the study.

The Investigator must report any pregnancy to Allakos within 24 hours of becoming aware of it, using the provided pregnancy reporting forms. The patient must be immediately discontinued from study drug. An uncomplicated pregnancy will not be considered an adverse event or serious adverse event, but all pregnancies will be followed through term.

Any congenital abnormalities noted at birth in the offspring of a patient who received study drug will be reported as a serious adverse event. The outcome of any pregnancy and the presence or absence of any congenital abnormality will be recorded in the source documentation and reported to the Medical Monitor and Sponsor.

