Patients will receive up to 26 monthly intravenous infusions of AK002 in an open-label manner. The first infusion of AK002 will be 1 mg/kg, and subsequent infusions will be 3 mg/kg.

If a monthly infusion of AK002 is missed the patient will be permitted to make up the missed dose after the 26th month so that all patients have the chance to receive a total of 26 infusions.

An EGD with biopsy will occur on Day 211 (± 3), Day 547 (± 3), and Day 729 (± 3) or 28 (± 3) days after the last dose of study drug, if early termination (ET) or if patient received additional missed doses.

Patients will be followed for 84 (± 3) days after the last dose of study drug. Follow-up visits will occur on Extension Day 736 (± 3), Day 757 (± 3), and Day 785 (± 3) or 35 (± 3), 56 (± 3), and 84 (± 3) days after last dose of study drug, if ET or if patient received additional missed doses.

Total duration of Study AK002-003X will be approximately 28 months if doses are administered monthly and none are missed, or longer, as needed for the patient to receive all 26 doses.

Approximately 60 patients will be enrolled in Study AK002-003X, based on enrollment of Study AK002-003.

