- 22) See [Appendix 19.8](#) for biopsy assessments. EGD should occur on Day 211 (± 3), Day 547 (± 3) and Day 729 (± 3) or 28 (± 3) days after the last dose of study drug if the patient discontinues the study early or if previous missed infusions were made up, and patient agrees to have an early-termination biopsy.
- 23) Non-serious adverse events will be captured from Day 1 (first dose of study drug) through Day 785 or 84 days after last dose of study drug, if ET or if previous missed infusions were made up.

Table 1 Notes cont.

- 24) Adverse events of special interest will be captured from Day 1 (first dose of study drug) through Day 785 or 84 days after last dose of study drug, if ET or if previous missed infusions were made up.
- 25) Serious adverse events of special interest will be captured from Day 1 (first dose of study drug) through Day 785 or 84 days after last dose of study drug, if ET or if previous missed infusions were made up.
- 26) Monthly doses # 3–8 will occur on Days 57, 85, 113, 141, 169, and 197 (± 3 days).
- 27) Monthly doses # 9–20 will occur on Days 225, 253, 281, 309, 337, 365, 393, 421, 449, 477, 505, and 533 (± 3 days).
- 28) Monthly doses # 21–26 will occur on Days 561, 589, 617, 645, 673, and 701 (± 3 days).
- 29) *Only if previous infusions have been missed*, make-up dosing may occur on Day 701 + 28 days (± 3), until 26 total doses have been administered.
- 30) Doses will be considered missed if they occur more than 15 days outside the protocol-specified window.

6. Criteria for Evaluation

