7.3 Inclusion Criteria

Patients are eligible for the study if all of the following criteria are met:

- 1) Provide written informed consent.
- 2) Completed Study AK002-003, defined as having received 4 infusions of study drug and followed through Day 113 (± 3) in Study AK002-003 or discontinued from treatment due to high eosinophil counts prior to infusions 2, 3, or 4, and willing to begin extended dosing on or about Day 113 (for AK002-003 completers) or within 6 months of last dosing for patients discontinued from treatment.
- 3) If patient is on pre-existing dietary restrictions, willingness to note any changes that occur from the Baseline diet, throughout the study.
- 4) Able and willing to comply with all study procedures.
- 5) Female patients must be either post-menopausal for at least 1 year or surgically sterile (tubal ligation, hysterectomy, or bilateral oophorectomy) for at least 3 months, or if of childbearing potential, have a negative pregnancy test and agree to use dual methods of contraception, or abstain from sexual activity until the end of the study, or for 120 days following the last dose of study drug, whichever is longer.
- 6) Male patients with female partners of childbearing potential must agree to use a highly effective method of contraception until the end of the study or for 120 days following the last dose of study drug, whichever is longer. All fertile men with female partners of childbearing potential should be instructed to contact the Investigator immediately if they suspect their partner might be pregnant at any time during study participation.

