7.4 Exclusion Criteria

Patients will be excluded from the study if they meet any of the following criteria:

- 1) Poor tolerance to previous administration of AK002 in the opinion of the Investigator.
- 2) Known hypersensitivity to any constituent of the study drug.
- 3) Any disease, condition (medical or surgical), or cardiac abnormality, which, in the opinion of the Investigator, would place the patient at increased risk.
- 4) Vaccination with live attenuated vaccines within 30 days prior to initiation of treatment in the study, during the treatment period, or vaccination expected within 5 half-lives (4 months) of study drug administration. All types and formulations of vaccines (including live attenuated vaccines) authorized by FDA or other regulatory authority for the prevention of COVID-19 may be administered before, during, or after this study. The vaccine should not be administered within 7 days prior to and within 7 days after the administration of AK002 so that any side effects caused by either of the 2 medications can be more easily determined.
- 5) Women who are pregnant, breastfeeding, or planning to become pregnant while participating in the study.
- 6) Any other reason that, in the opinion of the Investigator or Medical Monitor, makes the patient unsuitable for enrollment.
- 7) Diagnosis of Hypereosinophilic Syndrome (HES) based on standard criteria (blood eosinophils $>1500/\mu\text{L}$ with involvement of either the heart, nervous system, and/or bone marrow).

8. Concurrent Medications

Concomitant medications include both prescribed and over-the-counter medications and will be recorded in the electronic Case Report Forms (eCRF).

Any medication must have been stopped as required in AK002-003 exclusion criteria. Patients should be advised against taking any new medication, both prescribed and over-the-counter, without consulting the Investigator, unless the new medication is required for emergency use. Immediately prior to the first infusion, the study site personnel should ensure that the patient continues to meet the inclusion criteria and none of the exclusion criteria (including no receipt or use of prohibited medications).

All medications taken during participation in this study must be documented on the eCRF. All medications used to treat IRR or AE must also be documented.

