11.4.3 Pregnancy Test

Women of childbearing ability will provide a urine sample for on-site pregnancy (human chorionic gonadotropin) testing. The site will perform the urine pregnancy test using an indicator stick from the pregnancy test kit supplied by the central laboratory. This test will be assessed prior to the start of each study drug infusion. A pregnancy test will also be performed on Extension Day 736 or 35 (± 3) days after last dose, if ET or if previous missed infusions were made up.

For the purposes of the study, patients with FSH levels ≤ 30 mIU/mL should receive pregnancy testing.

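### Pregnancy capture ends 84 days after the last dose, 36 days before the contraception period ends, and nothing is scheduled that would find conceptions in between

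*Combined protocol and SAP*

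**What the plan says.** **Capture window.** Section 13.7.3 collects pregnancies in female patients and in the partners of male patients, over a window worded as "first exposed to the investigational product through Extension Day 785 or 84"; the 84 counts days (±3) from the last dose. The 84-day limit applies after early termination or when missed doses are made up.

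**Contraception period.** Inclusion criterion 5 (Section 7.3, repeated in the synopsis) asks women of childbearing potential to use dual contraception or to "abstain from sexual activity until the end of the study, or for 120 days following the last dose of study drug, whichever is longer". Criterion 6 sets the same period for men whose partners could become pregnant: "highly effective method of contraception until the end of the study or for 120 days following the last dose of study drug, whichever is longer".

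**Follow-up.** Section 5.1: "Patients will be followed for 84 (± 3) days after the last dose of study drug". No visit or contact is scheduled after that.

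**Testing.** Women of childbearing potential are tested before each infusion. Section 11.4.3 then adds one last test: "A pregnancy test will also be performed on Extension Day 736 or 35" (±3) days after the last dose. Table 1 and Section 12.12 list no test at the Day 757 or Day 785 visits.

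**Duty to notify.** Section 13.7.3 asks patients to tell the investigator about a pregnancy that occurs during the study. Criterion 6 likewise ties the man's duty to the time he is taking part.

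**Sentences without an end date.** Section 13.7.3 also requires the investigator to report any pregnancy to the sponsor within 24 hours of learning of it, and to report congenital abnormalities in the offspring of treated patients as serious adverse events. It says that all pregnancies will be followed to term.

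**The concern.** The protocol asks patients to avoid conception during a period in which it does not plan to collect conceptions. If one occurs late in that period, the patient has already had the last visit, the last pregnancy test is months past, and the instruction to notify covers only pregnancies during the study. The site would learn of it only by chance.

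What is at stake is individual case data. Section 13.7.3 gives pregnancies their own reporting form, a 24-hour deadline and follow-up to term. In a program with a little over 300 people enrolled to date across all its studies, including healthy volunteers, each exposed pregnancy is informative.

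The section is also open to two readings. Its opening sentence limits which pregnancies are captured, while later sentences speak of any or all pregnancies. Two sites could handle the same late pregnancy differently.

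**Working it through.** **Inputs**
- Dosing every 28 days, 26 doses, starting on Day 1 (Section 9.4). Table 1 notes: "Monthly doses # 21–26 will occur on Days 561, 589, 617, 645, 673, and 701 (± 3 days").
- End of pregnancy capture: Day 785, or 84 (±3) days after the last dose (Section 13.7.3).
- Contraception: end of study or 120 days after the last dose, whichever is longer (Section 7.3, criteria 5 and 6).
- Last scheduled pregnancy test: 35 (±3) days after the last dose (Section 11.4.3).
- About 60 patients (Section 15.1).

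**1. Reproduce the plan's own day.** Last dose = 1 + 25 × 28 = Day 701. End of capture = 701 + 84 = Day 785, as stated.

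**2. Which limit governs contraception.** Individual follow-up ends at 84 days and 84 < 120, so the 120-day limit is the longer one. It ends on 701 + 120 = Day 821.

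**3. Size of the gap.** 120 − 84 = 36 days (821 − 785 = 36). With the ±3-day visit window: 120 − 87 = 33 to 120 − 81 = 39 days. Make-up doses move both end points together, so the gap does not change.

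**4. Time without a test.** From the last test to the last visit: 84 − 35 = 49 days. From the last test to the end of contraception: 120 − 35 = 85 days. A conception shortly before Day 785 is inside the capture window but may not be recognized by that visit.

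**5. Share of the period.** 36/120 = 30% of the period after the last dose, but 36/821 = 4.4% of the whole period from Day 1.

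**6. Expected events.** The documents give no conception rate, so this step rests on an assumed range of 1 to 10 conceptions per 100 person-years under required contraception or abstinence. If all 60 patients were at risk, which overstates it, person-time = 60 × 36/365.25 = 5.9 person-years. Expected conceptions = 5.9 × 0.01 to 5.9 × 0.10, or about 0.06 to 0.6.

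**7. Half-life cross-check (not needed for the finding).** Exclusion criterion 4 refers to "vaccination expected within 5 half-lives (4 months) of study drug administration". Four months is 112 days at 28 days per month, 120 at 30 and 124 at 31. Dividing by 5 gives an implied half-life of 22.4, 24.0 or 24.8 days. The 120-day contraception period lies within that range.

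**The case against.** The strongest reply is that nothing here is a contradiction. The 84-day limit is the common cut-off for adverse events, serious adverse events, events of special interest and concomitant medication, and a precaution may reasonably outlast a reporting window. No endpoint or planned analysis uses pregnancy data, an uncomplicated pregnancy is not counted as an adverse event, and fewer than one event is expected. All of this stands and limits the severity. It does not supply any means of detecting a late pregnancy.

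Two stronger readings are tempting, and the documents support neither.

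First, a reader might infer that pregnancies after Day 785 are never reported or are discarded. Section 13.7.3 does not say that. Its sentences on any pregnancy and on congenital abnormalities have no end date, so a late pregnancy known to the site could still be reported. This safeguard is partial: it depends on the site finding out, and Section 13.2 ends the recording of serious adverse events at the same 84 days.

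Second, a reader might infer that the protocol itself defines 120 days as five half-lives of exposure risk, and go on to calculate how much drug remains at Day 84. The half-life wording appears only in the live-vaccine rule (Sections 7.4 and 8.1 and the synopsis) and the 120 days only in the contraception criteria. The figures are compatible, but the protocol does not link them. The readable text gives no human half-life in days, so any residual-drug percentage would rest on an assumed half-life of about 22 to 25 days and on simple first-order elimination.

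**Conclusion.** The mismatch is real and follows from Sections 13.7.3 and 7.3 alone. Active pregnancy ascertainment ends 36 days (33 to 39) before the contraception period does, and no other provision closes the gap.

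This is a minor to moderate gap in safety data. It changes no planned analysis. The expected number of missed conceptions is below one, and probably well below, given the assumed rates and the overstatement of treating every patient as at risk.

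The 36 days assume that the end of the study in criteria 5 and 6 means the patient's own last follow-up visit. If it meant the end of the whole trial, the contraception period could run longer for some patients and the gap would be larger. The finding needs no half-life, and it takes no position on how long contraception should last.

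**What to change.** Reconcile Section 13.7.3 with the contraception period in inclusion criteria 5 and 6, as a change to data collection only:

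1. Extend the pregnancy-reporting window to the end of that contraception period, for female patients and for partners of male patients.
2. At the last visit, instruct patients to report any pregnancy through that date, since the present instruction covers only the study itself.
3. Add one telephone contact at the end of the period, and state whether it counts toward study completion (Section 14.1).

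A call at that point will still miss conceptions too recent to be recognized. The instruction can ask patients to report those when they become known. If the sponsor prefers to keep 84 days, the protocol should give the reason and say how a later pregnancy is to be handled.

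The cost is a sentence or two, a line in Table 1 and one call per patient, about 60 calls. Section 17.1 also requires written sponsor agreement, submission to the health authority, IRB approval and the investigator's signature, so it would be sensible to include the change in the next amendment.

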13.7.4 Adverse Event of Special Interest Reporting

Beginning from the time of first study drug infusion and ending at Extension Day 785 or 84 (± 3) days after last dose of study drug if early termination or if missed doses are being made up, any new AESI (or new information related to a previously reported AESI) must be recorded in the Adverse Event eCRF and designated as an “adverse event of special interest.”

An AESI that also qualifies as a SAE (per Section 13.2) must also be reported as a SAE in accordance with Section 13.7.2. Adverse events of special interest that are also SAE must be recorded in the Adverse Event eCRF and designated as both “serious” and as an “adverse event of special interest.” These will be reported on the Sponsor-provided SAE forms and should be reported to the Sponsor within 24 hours of site awareness.

13.9 Study Withdrawal Criteria

Patients will be discontinued from the study in the event that:

- Occurrence of an exclusion criterion, which is clinically relevant and affects the patient's safety, if discontinuation is considered necessary by the Investigator and/or Sponsor.
- Rebounding of eosinophil counts to $>1500/\mu\text{L}$ in patients who entered the study with eosinophil levels $>1500/\mu\text{L}$, had an IRR during the first and/or second infusions, and whose eosinophil counts were initially suppressed after study drug will be withdrawn from the study.
- Serum transaminases (alanine aminotransferase and/or aspartate aminotransferase) $>3 \times$ upper limit of normal (ULN) and total bilirubin $>2 \times$ ULN (confirmed by subsequent repeat) without an alternative explanation.
- Elevation of alanine aminotransferase or aspartate aminotransferase $>3 \times$ ULN (confirmed by repeat) with the appearance or worsening of symptoms felt by the Investigator to be potentially related to hepatic inflammation, such as fatigue, nausea, vomiting, right upper quadrant pain or tenderness, fever, and rash.

13.10 Study Stopping Rules

The study may be discontinued prematurely in the event of any of the following:

- A life-threatening AE that is possibly or probably related to treatment.
- A fatal AE that is possibly or probably related to treatment.
- New information leading to unfavorable risk-benefit judgment of the study drug.
- Sponsor's decision that continuation of the study is unjustifiable for medical or ethical reasons.
- Discontinuation of development of the Sponsor's study drug.

Health Authorities and IRBs will be informed about the discontinuation of the study in accordance with applicable regulations. The study may be terminated or suspended on request of Health Authorities or Sponsor.

14. Discontinuation and Replacement of Patients

